7.2 Method of Treatment Assignment

After the participant’s initial eligibility is established and informed consent has been obtained, the participant must be entered into the study via the IRT to obtain a participant number. Specific instructions for using the IRT will be provided to the investigational site in a separate document. The investigator or designee will register the participant for screening by following the screening procedures established by BMS.

Once it is determined that the participant meets the eligibility criteria following screening, participant will be centrally randomized through the IRT.

The study will not allow participant replacement due to an AE.

7.3 Blinding

This is a randomized double-blinded study. Access to treatment codes will be restricted from all participants, and site and BMS personnel prior to database lock, with exceptions as specified below.

Blinding of treatment assignment is critical to the integrity of this clinical study. However, in the event of a medical emergency or pregnancy in an individual participant in which knowledge of the investigational product is critical to the participant's management, the blind for that participant may be broken by the investigator. The participant’s safety takes priority over any other considerations in determining if a treatment assignment should be unblinded.

Before breaking the blind of an individual participant's treatment, the investigator should determine that the unblinded information is necessary, ie, that it will alter the participant's immediate management. In many cases, particularly when the emergency is clearly not related to the investigational product, the problem may be properly managed by assuming that the participant is receiving active product. It is highly desirable that the decision to unblind treatment assignment be discussed with the Medical Monitor, but the investigator always has ultimate authority for the decision to unblind. The actual task of unblinding can be delegated by the investigator to a designee assigned the task on the Delegation of Authority. The Principal Investigator or appointed designee should only call in for emergency unblinding AFTER the decision to unblind the participant has been documented.

For this study, the method of unblinding for emergency purposes is through the IRT system. In case of an emergency, the investigator has unrestricted access to randomization information via IRT and can break the blind through the IRT system without prior approval from the Sponsor.

After the unblinding, the investigator shall notify the Medical Monitor and/or Study Director. The method of unblinding for emergency purposes is described in the IRT Manual. Participant and

unblinded treatment information and the reason for the blind being broken must be recorded on the appropriate study status page of the electronic case report form (eCRF).

In cases of accidental unblinding, contact the Medical Monitor and ensure every attempt is made to preserve the blind.

Any request to unblind a participant for non-emergency purposes should be discussed with the Medical Monitor.

Designated staff of Bristol Myers Squibb Company may be unblinded (obtain the randomization codes) prior to database lock to facilitate the bioanalytical analysis of pharmacokinetic samples and immunogenicity. A bioanalytical scientist in the Bioanalytical Sciences department of Bristol Myers Squibb Company (or a designee in the external central bioanalytical laboratory) will be unblinded to (may obtain) the randomized treatment assignments in order to minimize unnecessary bioanalytical analysis of samples.

7.4 Dosage Modification

There is no provision for dose modification of study treatment. If a participant interrupts treatment due to an AE, study treatment can be restarted in consultation with the Medical Monitor.

A Pharmacy Manual will not be provided for studies with oral dose formulations.

Dose reductions or dose escalations are not permitted. All dose modification rules apply to all arms given the blinded nature of this study.

7.5 Preparation/Handling/Storage/Accountability

The investigational product should be stored in a secure area according to local regulations. It is the responsibility of the investigator to ensure that investigational product is only dispensed to study Participants. The investigational product must be dispensed only from official study sites by authorized personnel according to local regulations.

The product storage manager should ensure that the study treatment is stored in accordance with the environmental conditions (temperature, light, and humidity) as determined by BMS. If concerns regarding the quality or appearance of the study treatment arise, the study treatment should not be dispensed and contact BMS immediately.

Study treatment not supplied by BMS will be stored in accordance with the package insert.

Investigational product documentation (whether supplied by BMS or not) must be maintained that includes all processes required to ensure drug is accurately administered. This includes documentation of drug storage, administration and, as applicable, storage temperatures, reconstitution, and use of required processes (eg, required diluents, administration sets).

Further guidance and information for final disposition of unused study treatment are provided in [Appendix 2](#).

7.5.1 Retained Samples for Bioavailability / Bioequivalence / Biocomparability

Not applicable.

7.6 Treatment Compliance

Study treatment compliance will be periodically monitored by drug accountability (Section 2). Drug accountability should be reviewed by the site study staff at each visit to confirm treatment compliance. Sites should discuss discrepancies with the participant at each on-treatment study visit.

The study shall be conducted as described in this approved protocol. All revisions to the protocol must be discussed with, and be prepared by BMS. The investigator should not implement any deviation or change to the protocol without prior review and documented approval/favorable opinion from the Institutional Review Board (IRB)/Independent Ethics Committee (IEC) of an amendment, except where necessary to eliminate an immediate hazard(s) to study participants.

7.7 Concomitant Therapy

7.7.1 Prohibited and/or Restricted Treatments

Prohibited and/or restricted medications taken prior to or during the study (up through Study Day 149) are described below. Medications taken within 4 weeks prior to Screening must be recorded on the eCRF.

- 1) Use of Class Ia and class III antiarrhythmic agents.
- 2) Table 7.7.1-1 presents prohibited and/or restricted potential medications.

Table 7.7.1-1: Prohibited and Restricted Medications

Type of Medication	Examples (not exhaustive)	Restriction	Required Washout
Allergen immunotherapy	various intradermal or sublingual	Prohibited during the study	4 months prior to randomization
Anticoagulants or antiplatelet agents	aspirin, clopidogrel, ticlopidine, warfarin, heparin, apixaban, etc.	Prohibited during the study	2 weeks or effective post-discontinuation PD duration (whichever is longer) prior to randomization
Antihistamines - except fexofenadine	Diphenhydramine, loratadine	Stable dose during the screening period; consistent use through the treatment period	Not applicable
Biologics	Belimumab, dupilumab, or omalizumab	Prohibited during the study	6 months prior to randomization
	Abatacept	Prohibited during the study	6 months prior to randomization
	Other biologics, including tocilizumab, anakinra	Prohibited during the study	8 weeks prior to screening

Table 7.7.1-1: Prohibited and Restricted Medications

Type of Medication	Examples (not exhaustive)	Restriction	Required Washout
	Intravenous Immunoglobulin	Prohibited during the study	8 weeks prior to screening
Bronchodilators -inhaled	Albuterol, salmeterol, ipratropium bromide	Stable dose during screening and through treatment period	Not applicable
BTK inhibitors	Marketed drugs, eg, ibrutinib, acalabrutinib Experimental drugs, eg, tirabrutinib, vecabrutinib, zanibrutinib, ARQ-531, GDC-0853, and any others	Prohibited lifetime use	Not applicable
Calcineurin-inhibitor -Topical	cyclosporine, tacrolimus	Prohibited during the study	4 weeks prior to randomization
Corticosteroid -Inhaled, oral non-absorbable or modified-release	Budesonide, fluticasone	Must follow stable regimen throughout study; cannot be used on as-needed basis	Not applicable
Corticosteroid -Systemic	IM, IA, intrabursal, IV Prednisone, dexamethasone	Prohibited during the study	4 weeks prior to randomization
Corticosteroid -Topical	Fluocinolone, hydrocortisone	As rescue therapy until Week 4 as detailed in Section 7.7.2	3 weeks prior to randomization
CYP2C8 and CYP3A4 -Strong or moderate inhibitors	clopidogrel, gemfibrozil, clarithromycin, itraconazole	Prohibited during the study	5 PK half-lives or 14 days of randomization
CYP2C8 and CYP3A4 -Strong or moderate inducers	rifampin, phenytoin	Prohibited during the study	3 weeks of the randomization
CYP2C8 or P-gp Sensitive substrates with narrow therapeutic indices	Repaglinide, dabigatran, fexofenadine	Prohibited during the study (digoxin allowed under limited/urgent circumstances; see below)	5 PK half-lives or 14 days of randomization
Immunization against agents other than influenza or SARS-CoV-2	Live vaccines	Prohibited during the study	90 days before and 60 days after EOT
	Nonlive vaccines unassociated with influenza or SARS-CoV-2		30 days before and 60 days after EOT

Table 7.7.1-1: Prohibited and Restricted Medications

Type of Medication	Examples (not exhaustive)	Restriction	Required Washout
Immunization for influenza or SARS-CoV-2	Live vaccines	Prohibited during the study	90 days before and 60 days after EOT
	Nonlive vaccines for influenza or SARS-CoV-2		14 days prior to screening and 60 days after EOT
Immunosuppressants -systemic or oral preparations of herbal immunomodulatory medications	Mycophenolate-mofetil, azathioprine, methotrexate	Prohibited during the study	8 weeks prior to randomization
JAK inhibitors	Tofacitinib, baricitinib, filgotinib, and upadacitinib	Prohibited during the study	8 weeks prior to randomization
Leukotriene inhibitors	montelukast	Prohibited during the study	4 weeks prior to randomization
Monoamine Oxidase Inhibitors	Selegiline, phenelzine	Prohibited during the study	2 weeks prior to randomization
Narcotic analgesics	Oxycodone and, hydrocodone	Prohibited during the study	Not applicable
Non-narcotic analgesics	Acetaminophen	Brief courses for up to 7 days allowed	Not applicable
Phosphodiesterase Inhibitor	Apremilast, crisaborole	Prohibited during the study	3 weeks prior to randomization
Phototherapy	UVB, UVA	Prohibited during the study	4 weeks prior to randomization
S1P Receptor Modulators	Fingolimod, ozanimod, siponimod, etrasimod	Prohibited lifetime use	Not applicable
Treatments to be restricted or suspended during the study	rosiglitazone	Dose up to 4 mg can be used, monitor glucose closely	Not applicable
	torasemide	Dose up to 10 mg can be used	Not applicable
	digoxin	For acute use only, exclude at baseline; limit highest dose and monitor trough concentrations; stop treatment with IP during treatment with digoxin and for 3 days afterwards	Not applicable
Treatments -Other	Diquafosol, rebamipide	Prohibited during the study	4 weeks prior to randomization

No concomitant medications (prescription, over-the-counter or herbal) are to be administered during study unless they are prescribed for treatment of specific clinical events. Any concomitant therapies must be recorded on the eCRF, along with the reason for its administration.

The investigator should contact and confirm agreement with the BMS medical monitor (and acknowledgement from the contract research organization medical monitor) prior to the administration of any concomitant medications, excepting those needed for urgent/emergent treatment for which there is insufficient time for such contact.

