6 STUDY POPULATION

For entry into the study, the following criteria MUST be met.

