- a) High likelihood - based on participant history, and investigator judgement – of requiring rescue therapy in < 4 weeks prior to randomization (see [Section 7.7.2](#))
- b) Evidence of acute flare between the Screening and Baseline/ Randomization (eg, doubling of the EASI score between Screening and Baseline, or worsening that requires administration of prohibited medications).
- c) Skin lesion(s) and/or pruritus due to conditions other than AD that would interfere with the study specified assessments.

4) Prior/Concomitant Therapy

- a) Treatment with anticoagulant or antiplatelet therapies, including aspirin for cardioprotection, within 2 weeks prior to randomization or during the study.

- b) AD-related prescription or over-the-counter skin barrier treatments (eg, Cerave, Epicerum, etc.) therapy within 2 weeks prior to randomization
- c) Any bleach baths within 2 weeks prior to randomization
- d) Monoamine oxidase inhibitors (eg, selegiline, phenelzine) within 2 weeks prior to randomization
- e) Use of strong or moderate inhibitors or inducers of CYP2C8 or CYP3A4 within the longer of 5 PK half-lives or 14 days prior to randomization (inhibitors), or within 3 weeks prior to randomization (inducers).
 - i) Please refer to [Table 7.7.1-1](#) for examples.
 - ii) Sponsor's Medical Monitor should be consulted for any uncertainties regarding CYP2C8 or CYP3A4 modulators.
- f) Phosphodiesterase-4 (PDE4) inhibitors within 3 weeks prior to randomization.
- g) Use of phototherapy (ie, UVB, UVA) within 4 weeks prior to randomization.
- h) Leukotriene inhibitor treatment within 4 weeks prior to randomization.
- i) Diquafosol or rebamipide therapy within 4 weeks prior to randomization.
- j) Systemic corticosteroid treatment within 4 weeks prior to randomization.
- k) Systemic immunosuppressive drugs (CsA, MMF, AZA, MTX) or oral preparations of herbal immunomodulatory medications within 8 weeks prior to randomization.
- l) Exposure to JAK inhibitors such as tofacitinib, baricitinib, filgotinib, or upadacitinib within 8 weeks prior to randomization.
- m) Intravenous (IV) immunoglobulin within 8 weeks prior to randomization or during the study.
- n) Allergen immunotherapy within 4 months of randomization.
- o) Biologics depending on the type:
 - i) Cell-depleting agents, including rituximab: within 6 months, or until the targeted population (eg, CD19+ lymphocyte counts for rituximab) returns to normal, whichever is longer

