 - ii) Biologics such as tocilizumab and anakinra within 8 weeks prior to randomization
 - iii) Other biologics: within the longer of 5 half-lives (if known) or 6 months of randomization (eg. dupilumab)
- p) Prior exposure to BTK inhibitors such as ibrutinib, acalabrutinib, or experimental drugs (eg, BMS-986166 or branebrutinib, tirabrutinib, vecabrutinib, zanibrutinib, ARQ-531, GDC-0853, or others) at any time.
- q) Prior exposure to S1PR modulators (eg, fingolimod, etrasimod, ozanimod, etc.) at any time.

- r) Use of any immunomodulator or investigational drug not listed above within the longer of 5 PK half-lives, 5 PD half-lives, or 6 months of randomization.

5) Laboratory Test and Procedural Findings

- a) The following test findings at Screening or Baseline
- i) WBC count < 3000/ μ L or > 14,000/ μ L
 - ii) ANC < the lower of: lower limit of normal (LLN) or 1500/ μ L
 - iii) ALC < 1000/ μ L
 - iv) Platelet count < 100,000/ μ L
 - v) Serum creatinine > 2 mg/dL
 - vi) Estimated glomerular filtration rate (eGFR) < 60 mL/min/1.73 m² as calculated using the Chronic Kidney Disease Epidemiology Collaboration (CKD-EPI) equation¹¹⁰:
$$\text{eGFR} = 141 \times \min(\text{Scr}/\kappa, 1)^\alpha \times \max(\text{Scr}/\kappa, 1)^{-1.209} \times 0.993^{\text{Age}} \times 1.018 [\text{if female}] \times 1.159 [\text{if black}]$$
-- where Scr is serum creatinine, κ is 0.7 for females and 0.9 for males, α is -0.329 for females and -0.411 for males, min indicates the minimum of Scr/ κ or 1, and max indicates the maximum of Scr/ κ or 1.
 - vii) AST or ALT >1.5x ULN
 - viii) Total bilirubin > 2 mg/dL (34 μ mol/L)
 - ix) Hemoglobin <10 g/dL
 - x) ECG: HR < 55 bpm; PR \geq 210 msec; QRS \geq 120 msec; QTcF >450 msec males, > 470 msec females, or any clinically significant heart conduction abnormality (eg, left bundle branch block, atrial fibrillation).
 - xi) Abnormality on posteroanterior + lateral chest radiograph, taken during the Screening period that is relevant to safe conduct of this study.
 - xii) Abnormality on optical coherence tomography (OCT) testing suggestive of macular or choroidal pathology beyond that expected for a healthy person of the participant's age.
 - xiii) Heart rate < 55 bpm or > 95 bpm at rest
 - xiv) Blood pressure > Grade 1 hypertension (> 159 mmHg systolic and > 99 mmHg diastolic) according to the 2018 European Society of Cardiology/European Society of Hypertension guidelines for the management of arterial hypertension¹¹¹

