 - xv) Any other clinically significant laboratory or procedure abnormalities that, in the opinion of the investigator, might pose unacceptable risk to the participant during the study.

6) Other Exclusion Criteria

- a) Use of a tanning booth/parlor or significant change in sun exposure within 4 weeks of the Screening visit.

- b) Onset of a new exercise routine or major change to a previous exercise routine within 2 weeks prior to randomization.
- c) Prisoners or participants who are involuntarily incarcerated. (Note: under certain specific circumstances and participant to local law a person who has been imprisoned after enrollment may be permitted to continue as a participant. Strict conditions apply and Bristol Myers Squibb approval is required.)
- d) Employment by the Sponsor, clinical research organizations, or study site.
- e) Participants who are compulsorily detained for treatment of either a psychiatric or physical (eg, infectious disease) illness.
- f) Recent (within 6 months of study drug administration) drug or alcohol abuse as defined in DSM-5, Diagnostic Criteria for Drug and Alcohol Abuse ([Appendix 7](#))
- g) Inability to comply with restrictions as listed in [Section 6.3](#) and prohibited/restricted treatments in [Section 7.7.1](#).
- h) Inability to tolerate oral medication.
- i) Inability to be venipunctured and/or tolerate venous access.

Eligibility criteria for this study have been carefully considered to ensure the safety of the study participants and that the results of the study can be used. It is imperative that participants fully meet all eligibility criteria.

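### Table 7.7.1-1 prints an 8-week washout for other biologics where exclusion 4)o)iii requires at least 6 months

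*Combined protocol and SAP*

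**What the plan says.** Two current sections set washouts for prior biologics.

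**Section 7.7.1, Table 7.7.1-1.** Belimumab, dupilumab and omalizumab share a row at 6 months before randomization, and abatacept has its own row at the same period. The next row, "Other biologics, including tocilizumab, anakinra", has a required washout of 8 weeks, counted back from screening.

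**Section 6.2, exclusion 4)o).** This splits biologics into three groups:
- 4)o)i: "Cell-depleting agents, including rituximab: within 6 months, or until the targeted population (eg, CD19+ lymphocyte counts for rituximab) returns to normal, whichever is longer"
- 4)o)ii: "Biologics such as tocilizumab and anakinra within 8 weeks prior to randomization"
- 4)o)iii: "Other biologics: within the longer of 5 half-lives (if known) or 6 months of randomization (eg. dupilumab"

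On precedence, Section 6 opens with "For entry into the study, the following criteria MUST be met" and Section 6.2 closes with "It is imperative that participants fully meet all eligibility criteria". Section 9 requires eligibility to be confirmed before randomization and allows no waivers.

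**The concern.** The same label carries two different washouts. Exclusion 4)o) separates the 8-week agents from the remaining biologics. The table puts both in one row and gives that row the shorter period. Its column is headed as a required washout, so the 8 weeks reads as an operative rule.

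A site may consult the table when it reviews a candidate's treatment history. If it stopped there, it could enrol someone whose last dose of an unnamed biologic lies inside the period that 4)o)iii excludes. That would be an eligibility deviation. Any residual effect of the biologic could also overlap with a study drug that the protocol itself describes as immunosuppressive by mechanism.

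Recent biologic use is plausible in this population. Inclusion 2)f in Section 6.1 counts inadequate control on biologics in the 6 months before randomization as a qualifying history. Section 7.7.1 requires eCRF recording only of medications taken in the 4 weeks before screening, so a dose in the gap falls outside that requirement. Detection is still possible, because Table 2-1 collects prior medication and AD-related treatment history at screening.

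**Working it through.** The 8 weeks is a printed rule, so there is no plan calculation to reproduce. The check puts both rules on one time scale, days before randomization (Day 1).

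**Inputs**
- Table washout: 8 weeks before screening (Table 7.7.1-1).
- Screening: Day -35 to Day -1, which adds 1 to 35 days (Table 2-1 and Section 5.1.1).
- Exclusion 4)o)iii: a floor of 6 months before randomization (Section 6.2).
- Assumption: 6 months = 182 days. The calendar range of 181 to 184 days is also shown.

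**Table rule, counted from randomization**
- 8 × 7 = 56 days before screening.
- Shortest: 56 + 1 = 57 days. Longest: 56 + 35 = 91 days.

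**Shortfall against the 4)o)iii floor** (6 months minus the table rule)
- 35-day screening: 182 − 91 = 91 days = 13.0 weeks.
- 1-day screening: 182 − 57 = 125 days = 17.9 weeks.
- Extremes over 181 to 184 days: 181 − 91 = 90 days (12.9 weeks) and 184 − 57 = 127 days (18.1 weeks).

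These are minimums, because 4)o)iii takes the longer of two periods. Five half-lives exceed 182 days once the half-life is above 182 / 5 = 36.4 days.

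**Agents named in the two sections**

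| Agent | Table 7.7.1-1 | Section 6.2 | Table shorter? |
|---|---|---|---|
| Tocilizumab, anakinra | 57–91 days | 56 days, 4)o)ii | No; table stricter by 1–35 days |
| Dupilumab, belimumab, omalizumab, abatacept | 6 months | 6-month floor, 4)o)iii | Not on the 6-month floor |
| Other biologics, no own row and outside 4)o)ii | 57–91 days | At least 182 days, 4)o)iii | Yes, by at least 91–125 days |

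The shortfall is confined to the last line.

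**The case against.** The strongest reply is that the controlling text already settles the matter. Section 6.2 must be met in full, and nothing says that satisfying the table's washout is sufficient for entry. A site that applies 4)o)iii excludes the patient whatever the table prints. This stands. A reader might infer that the table makes such patients eligible, but it does not.

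A second reply is that the row need not be a catch-all. The column describes its examples as not exhaustive, so the 6-month row that names dupilumab could extend to similar agents, and dupilumab is also the example in 4)o)iii. The 8-week row names the same two drugs as 4)o)ii, which is itself open-ended. On that reading the rows mirror 4)o)iii and 4)o)ii and the gap for a dupilumab-like agent disappears. This makes the size conditional on how the row is read. It does not remove the conflict: the plain sense of the row's label is everything not already listed, and 4)o)iii uses the same label with a longer period.

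A third reply is that sites are not clearly sent to the table for washouts. A reader might infer from exclusion 6)g, which cites Section 7.7.1, that sites will check eligibility against it. That criterion concerns inability to comply with restrictions. Exclusion 4)e)i does cite the table, but only for examples of CYP modulators, and 4)o) has no such reference. Sites may use the table; the documents do not show that they will.

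**Conclusion.** The point holds as a minor internal inconsistency that is wrong as written. For biologics with no row of their own and outside 4)o)ii, the printed washout is at least about 13 to 18 weeks shorter than 4)o)iii requires. This rests on the catch-all reading, on 6 months being about 182 days, and on a screening interval of 1 to 35 days. The wording of 4)o)ii leaves some doubt about which unnamed agents qualify for 8 weeks.

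The harm is limited to a site that relies on the table alone. The number of patients affected cannot be estimated from the documents.

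Three stronger conclusions that a reader might draw are not supported:
- That the table also misstates the washout for cell-depleting agents. It has no row for them and does not name rituximab. Placing them in the 8-week row is an inference from a missing row, not a wrong printed figure.
- That exclusion 4)r shows 6 months to be the intended default. It reads "Use of any immunomodulator or investigational drug not listed above within the longer of 5 PK half-lives" and so reaches only agents that are not already listed; biologics are listed before it. Inclusion 2)f also sits uneasily with a universal 6-month floor. The documents call for the two sections to be reconciled but do not settle what the sponsor intended.
- That the power or the EASI comparison is affected. Nothing in the documents supports this, and it is not claimed.

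**What to change.** In Table 7.7.1-1:
- Limit the 8-week row to the agents of 4)o)ii, labelled as biologics such as tocilizumab and anakinra.
- Add a row for the remaining biologics that matches 4)o)iii: 6 months before randomization, or 5 half-lives (where known) if longer.
- Optionally, for completeness, add a row repeating 4)o)i for cell-depleting agents.

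The cost is a table edit in the next amendment. Design, sample size and analysis do not change.
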